#### **6.1.6 Responsibility for completing and reporting the screening log**

The delegation log will record the individuals responsible for the completion and reporting of screening logs.

### **6.2 Clinically referred participants**

Potential participants will be identified from heart failure clinics, new referrals to the heart failure service, inpatient hospital admissions and referrals for invasive or CT coronary angiography. Site-specific trial teams will include dedicated heart failure specialists with links to local primary care and community heart failure teams to advertise the trial and encourage referral for screening and participation.

Potential participants will be approached by a member of their clinical team and given a basic explanation of the study. They will then be asked if they would like to speak to a member of the research team. All centres in the NIHR-funded UK HFpEF registry (NIHR301338) will be approached to identify potential participants and refer to the trial sites for participation.

The review of eligibility and initial approach to the patient must be made by a member of their direct care team. It is then dependent on the patient to contact the relevant trial site to undergo informed consent and any further study procedures.

#### **6.2.1 Self-referred participants**

Trial involvement will be advertised via posters, leaflets, the study website, NIHR Be Part of Research and community cardiac groups from which potential participants can self-refer. Participants will be

invited to contact a member of research staff at the trial site of their choosing via telephone, post or email. Consent will be sought to request clinical data to confirm trial eligibility, including echocardiographic features of HFpEF. Clinical research network-funded research nurses will retrieve clinical data from other NHS organisations to confirm eligibility and review this data with the PI.

### **6.3 Consent**

A member of the research team will contact all eligible patients to explain the study in detail and provide a participant information sheet (PIS). The PIS will be available in a number of common non-English languages. Participant information videos will also be made available.

The research team member will answer any question from the patient, as well as their family or friends if the patient requests their support in coming to a decision.

At least 24 hours will be allowed for the patient to discuss with family and/or friends and consider their decision to participate in the study.

Consent may be taken electronically or on a paper form, depending on the patient's preference.

All participants must provide informed consent prior to any trial activities taking place.

#### **6.3.1.1 Patients with impaired capacity**

Consideration has been given to patients with impaired capacity (Appendix 1). Whilst the ambition is always to provide maximally inclusive recruitment, given the complexity of the trial intervention (an invasive procedure under conscious sedation) it would not be appropriate to enrol participants who were not able to consent.

### **6.4 Randomisation**

Randomisation will be performed during the coronary angiography procedure, within the catheterisation laboratory, via a validated online web-based system (Sealed Envelope).

The randomised treatment allocation will be reported on the Sealed Envelope system and via e-mail to unblinded members of the research team. Treatment allocation will be concealed from all blinded team members.

The unblinded trial team will be notified of new randomisations via email.

#### **6.4.1 Stratification**

Treatment allocation will be stratified by site using randomly permuted blocks of varying size, with 1 to 1 allocation of participants between the PCI and placebo procedure arms.

#### **6.4.2 Participant identification log**

A list of all patients enrolled into the trial will be maintained by each recruiting site, containing participant identification numbers, full names, dates of birth and dates of enrolment in the trial, which could be used for unambiguous identification of each participant if required.

### **6.4.3 GP notification and medical records**

The patient's enrolment in the trial, without treatment allocation, must be recorded in the patient's medical record. The participant's general practitioner will also be notified, unless the participant specifically asks for them not to be informed.

## **6.5 Intervention**

### **6.5.1 Arranging the trial intervention**

The trial intervention will be performed during a day-case hospital admission. Potential dates for the procedure will be discussed with participants in order to find a suitable date for them, including fit notes for employers and funding for relief carers where the participant is a care provider.

### **6.5.2 On the day of the intervention**

On the day of the trial intervention, ongoing consent for the study will be confirmed and clinical consent for the invasive procedure obtained by the unblinded PI. Procedures will be performed by either the unblinded PI or an unblinded sub-investigator. Participants will receive pre-treatment with antiplatelet medication (aspirin 300mg and clopidogrel 300-600mg per local protocol). The KCCQ will be repeated to measure early changes in quality of life with medical optimisation.

Coronary angiography will be performed using standard procedure, preferentially via radial access. Following coronary angiography, a detailed physiological assessment will be performed in all target coronary arteries, including measures of fractional flow reserve (FFR), coronary flow reserve (CFR) and microvascular function. Left ventricular end diastolic pressure will be measured at rest and during handgrip exercise.

Before randomisation, patients will receive headphones playing music to ensure auditory isolation, and patients will be sedated using incremental doses of benzodiazepines and opiates to a deep level of conscious sedation.

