## **6.10 Schedule of assessments for each visit**

### **6.10.1 Baseline visit**

Eligible participants with HFpEF and significant coronary artery disease will attend one-stop outpatient HFpEF clinic and study visit. All investigations will be co-ordinated by the trial team to occur within this visit unless the person wishes otherwise in which case alternative arrangements will be made. Their visit will be supported by the trial research nurse, who will co-ordinate appointments and guide them through the procedures. During this visit the participant will have a clinical review by the unblinded PI, who will optimise their treatment for HFpEF and either manage or refer for optimal management of comorbidities, as per current treatment guidelines.

The participant will undergo the following baseline assessments:

- Measurement of vital signs
  - Heart rate
  - Blood pressure
  - Arterial oxygen saturations (pulse oximetry)
  - Weight
  - Height
- Medical history
  - Past medical history
  - Medication history
  - Social history
- Health status
  - Kansas City Cardiomyopathy Questionnaire
  - New York Heart Association functional class
  - Canadian Cardiac Society angina class
- Blood tests for cardiac biomarkers and pre-PCI testing
  - Full blood count
  - Full lipid profile
  - Renal function

- Troponin
- NT-pro-BNP
- 12-lead ECG
- Three-dimensional transthoracic echocardiogram

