## 16 STATISTICAL CONSIDERATIONS

A detailed statistical analysis plan will be written and signed off prior to database lock and unblinding of trial data. For the KCCQ-OSS and CFR measures, differences in mean levels of the outcome measures between treatment groups at the relevant timepoints will be calculated, together with 95% confidence intervals, using a linear mixed model with treatment group, categorical treatment by timepoint interaction and baseline outcome measures included in the model (random intercept, unstructured correlation). It may be necessary to examine the measures for transformations to adhere to the assumptions of the linear mixed model or use bootstrapping techniques if a suitable

transformation cannot be found. For the primary analysis, any patient who dies will be excluded but as a sensitivity analysis a value of 0 will be imputed. All analyses will be on an intention-to-treat basis. Key secondary outcomes include all-cause death and/or hospitalisation for heart failure which will be assessed and compared between groups with hazard ratios using a Cox proportional hazards model. In addition risk differences will also be presented together with 95% confidence intervals at 6 months. The individual components of all-cause-death and hospitalisation for heart failure will also be analysed. In addition, groups will be compared using the unpaired win ratio method with a prespecified hierarchy of all-cause death, hospitalisation for heart failure and difference in KCCQ-OSS  $\geq 7$  between participants at six months. Sensitivity analyses will be reported excluding any participants who underwent emergency unblinding. Whilst the sample size will not permit definitive analyses based upon subgroups, hypothesis generating subgroup analyses will be performed to assess for differential treatment response based on age, sex and baseline NT-pro-BNP.

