### **16.1 Sample size calculations**

In pilot data from our REVIVED-BCIS2 trial (which has been selected as calculations can be performed using individual participant data and represents the only randomised comparison of PCI to medical treatment in a heart failure population), the baseline KCCQ-OSS was 60.9 with a between-group difference at six months of 6.5 (95% confidence interval 3.5 to 9.5) points. There was a high degree of correlation between baseline and six-month scores (correlation coefficient: 0.67). Though the standard distributions of scores at each timepoint were non-normally and widely distributed, the distribution of change in score from baseline to follow-up was close to normally distributed. Assuming similar baseline values, a standard deviation of KCCQ-OSS of 25, correlation coefficient of 0.6 and an alpha of 0.05, a total of 350 participants are required to have in excess of 85% power to detect a minimum clinically important difference (MCID) of 7 points, allowing for 10% withdrawals or losses to follow-up. If correlation were higher (0.65) a sample size of 350 participants will achieve in excess of 90% power for a difference of 7. If the standard deviation were increased (27), we would retain in excess of 80% power for a MCID of 7. The inclusion of a three month follow-up timepoint will enable repeated measures of KCCQ-OSS which will further increase power. A review of the sample size assumptions blinded to treatment allocation will be made after 1 year of recruitment to assess the correlation between baseline and follow up measures; consideration will be given to extending the sample size at this point if recruitment permits.

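### The primary model should adjust for both pre-randomisation KCCQ-OSS scores, not only the one called baseline: efficiency is lost, but the sample size is not wrong

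*Protocol*

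**What the plan says.** The schedule in Protocol section 6.12 has KCCQ at the baseline visit, the procedural visit, three months and six months. Sections 6.4 and 6.5.3 place randomisation during coronary angiography in the catheterisation laboratory. Section 6.10.2 lists the procedure-day KCCQ as pre-PCI health status. Both of the first two scores therefore precede allocation.

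The table in section 6.8.1 lists them as separate forms, Baseline KCCQ and Pre-procedure KCCQ. At the baseline visit the participant is reviewed by the unblinded PI, "who will optimise their treatment for HFpEF" (section 6.10.1), and section 6.7 places optimisation of medical therapy at enrolment. The stated reason for the second questionnaire is: "The KCCQ will be repeated to measure early changes in quality of life with medical optimisation" (section 6.5.2).

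Section 16 specifies a linear mixed model with treatment, treatment by categorical timepoint, and "baseline outcome measures included in the model". Section 16.1 bases power on a single correlation between baseline and follow-up.

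**The concern.** A score measured before allocation can be used as a covariate without risk of bias from treatment, and its value depends on how well it predicts the six-month score. The protocol expects KCCQ to move between the two measurements, since that is why it repeats the questionnaire. The baseline-visit score is then the one more exposed to treatment changes that have not yet taken effect, yet it is the one that the word baseline points to.

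Two things are at stake. Precision available from data already collected may go unused. And if optimisation weakens the link between the baseline-visit score and the six-month score, the correlation of 0.6 behind the power statement may not hold for the covariate actually used.

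**Working it through.** **Inputs from section 16.1.** 350 randomised 1:1; 10% loss, so 350 × 0.9 / 2 = 157.5 per arm; difference 7 points; "a standard deviation of KCCQ-OSS of 25"; "correlation coefficient of 0.6 and an alpha of 0.05". The pilot data gave 0.67. Sidedness is not stated; two-sided 0.05 is assumed, in line with the 95% confidence intervals.

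**Inputs not in the protocol (assumed).** The correlation of the procedure-day score with the six-month score, and the correlation r12 between the two pre-randomisation scores.

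**Formulae.** Residual SD = SD × √(1 − R²). SE = residual SD × √(2/157.5). Power = Φ(7/SE − 1.96). With one covariate, R² = r². With two, R² = (r1² + r2² − 2·r1·r2·r12)/(1 − r12²).

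**Step 1: the plan's own figures.**
- SD 25, r = 0.6: residual SD 20.0, SE 2.254, 7/SE = 3.106, power 87.4% (plan: above 85%).
- SD 25, r = 0.65: residual SD 19.0, power 90.5% (plan: above 90%).
- SD 27, r = 0.6: residual SD 21.6, power 82.0% (plan: above 80%).

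All three reproduce with one baseline covariate.

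**Step 2: both scores, each correlated 0.6 with six months (SD 25).** R² reduces to 0.72/(1 + r12).

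| r12 | R² | Power | Evaluable participants giving the 87.4% that 315 give with one score |
|---|---|---|---|
| 0.6 | 0.450 | 91.8% | 272 |
| 0.7 | 0.424 | 90.5% | 284 |
| 0.8 | 0.400 | 89.4% | 296 |
| 0.9 | 0.379 | 88.4% | 306 |

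The gain is about 1 to 4 percentage points. At SD 27 the same range lifts power from 82.0% to between 83.1% and 87.3%.

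**Step 3: optimisation weakens the first score (r1 = 0.5, r2 = 0.65).**
- Earlier score alone: residual SD 25 × √0.75 = 21.65, SE 2.440, power 81.8%.
- Later score alone: R² = 0.4225, power 90.5%.
- Both, r12 = 0.75: R² = (0.25 + 0.4225 − 0.4875)/0.4375 = 0.4229, power 90.5%.

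Here nearly all the gain comes from using the later score. Adding the earlier one changes almost nothing at this r12.

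**Step 4: if instead the later score predicts less well (r1 = 0.6, r2 = 0.5, r12 = 0.7).** R² = (0.36 + 0.25 − 0.42)/0.51 = 0.3725, power 88.0%, against 87.4% with the earlier score alone and 81.8% with the later alone. Using both protects against not knowing which score is the better predictor.

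**The case against.** The strongest reply is that this is detail for the statistical analysis plan. Section 16 says such a plan will be written; its plural wording covers KCCQ-OSS and CFR and excludes no pre-randomisation score; and form names are not a definition of a model covariate. Part of this stands: the protocol does not forbid using the later score. But it names two distinct scores, uses the label of one of them in the model, and gives the other a different purpose, so a reader would take the earlier score as the covariate.

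It is also fair that the gain rests on correlations the protocol does not give. It states no interval between the two visits, so r12 could be high and the gain about one point. The fall to 0.5 is hypothetical, and the only evidence cited is the pilot value: "There was a high degree of correlation between baseline and six-month scores (correlation coefficient: 0.67". Section 16.1 also plans a blinded review after one year of recruitment of the correlation between baseline and follow-up scores, with possible extension of the sample. That guards partly against a weak correlation, although its remedy is more participants and depends on recruitment.

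Three stronger readings are tempting, and the documents do not support them.
- *The sample size is wrong.* It is not; all three stated powers reproduce.
- *Section 16.1 is wrong about the three-month visit.* It says only: "The inclusion of a three month follow-up timepoint will enable repeated measures of KCCQ-OSS which will further increase power". No size is claimed, and there can be an increase. With 10% missing at six months, a three-month score for every dropout, and an assumed correlation of 0.5 to 0.8 between the two follow-up scores given baseline, power goes from 87.4% to about 88–89%. The sentence can stand.
- *The win ratio is defective because it ignores baseline.* Its "prespecified hierarchy of all-cause death, hospitalisation for heart failure and difference in KCCQ-OSS" compares six-month scores by a margin of 7 points. Baseline adjustment would probably raise its power, but it is an additional analysis with no power claim, and a raw 7-point margin is a defensible, interpretable choice. A plain change score would not help in every case: in simulation with a correlation of 0.5 and no deaths or admissions it gave about 66% power against 68% for the raw score.

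**Conclusion.** The point holds as a modest, avoidable loss of efficiency in the primary analysis. Two valid pre-randomisation KCCQ-OSS scores are collected, and the model as worded points to the earlier one only. On the plan's inputs, power is 87.4% with one score at 0.6 and about 88% to 92% with both, for r12 from 0.9 down to 0.6. The larger exposure is conditional: about 82% with the earlier score alone against about 90% with the later, if their correlations with six months are 0.5 and 0.65. These correlations are assumptions. The calculation also treats the six-month contrast as an analysis of covariance with 315 evaluable participants.

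**What to change.** In section 16, state that the primary KCCQ-OSS model includes both pre-randomisation scores, from the baseline visit and from the procedure day, as covariates. Where a single baseline is needed, name the procedure-day score as the reference, with the baseline-visit score standing in when it is missing. Apply the same definition in the one-year blinded review of the correlation, so that the review assesses the covariates the model will use.

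The cost is wording, one rule for missing procedure-day scores and one extra model parameter; there is no new data collection or participant burden. The change should be fixed before unblinding, because a later choice between two baselines could look driven by the data. No change is needed to the sample size or to the three-month sentence. A baseline-adjusted KCCQ tier in the win ratio is at most an optional sensitivity analysis.

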### **6.5.3 Timing of randomisation**

During the coronary angiography procedure, the participant will be randomised 1:1 to either PCI or placebo procedure using the online randomisation system.

### **6.5.4 Delivering the randomised treatment allocation**

#### **6.5.4.1 Participants randomised to PCI**

In patients assigned to PCI, angioplasty and stenting will be attempted to all significant coronary stenoses as determined by the CT-FFR or FFR measurements. Contemporary best practice including the use of intracoronary imaging is mandated. The default approach will be to implant drug eluting stents, but drug coated balloon angioplasty is permitted in selected cases in accordance with the current evidence base and guidelines. Operators will achieve as much revascularisation as can safely be delivered in a timeframe which maintains blinding; if incomplete revascularisation is necessary, operators will target treatment to the most haemodynamically significant lesions subtending the largest territories. Staged procedures are not permitted, as they would invalidate blinding. Target

lesion success will be defined by a residual stenosis <10% on angiography with Thrombolysis In Myocardial Infarction (TIMI) 3 flow.

#### **6.5.4.2 Participants randomised to placebo procedure**

In the placebo procedure group, participants will undergo a placebo stent procedure that involves placement of a catheter but does not involve deployment of an actual stent. Over a period of 30 minutes, movements of the image intensifier, screen display and personnel will simulate a PCI procedure.

#### **6.5.5 Post-intervention**

At the end of the procedure the participant will be transferred to the recovery unit and observed until the effects of sedation are fully reversed and the patient is back to their baseline condition.

#### **6.5.6 Prescription of anticoagulants**

Participants who are not receiving an oral anticoagulant (OAC) will be prescribed long-term aspirin 75mg once daily from the day following the procedure. Participants who are receiving an OAC will be prescribed aspirin 75mg once daily for one week from the day following the procedure.

### **6.6 Prescription of clopidogrel or placebo clopidogrel**

Participants randomised to PCI will receive clopidogrel at a dose of 75mg OD, to be taken for up to 6 months following PCI. Participants randomised to the placebo procedure will receive matching placebo clopidogrel tablets, to be taken for up to 6 months following PCI. The duration of clopidogrel or placebo clopidogrel will be determined by individual bleeding risk.

Clopidogrel and matching placebo clopidogrel tablets will be manufactured by Guy's and St Thomas' Pharmacy Manufacturing Unit (PMU) located on the [name].

### **6.7 Medical therapy**

All participants will receive guideline directed medical therapy for HFpEF. All participants will be prescribed a SGLT-2i unless there are specific contraindications or the participant declines treatment. Participants who are obese will be offered treatment with a GLP-1 agonist. Loop diuretics will be prescribed as dictated by fluid status. The protocol for medical therapy will be updated as further agents are adopted into clinical guidelines (e.g. finerenone). This medical therapy will be optimised at the time of enrolment and will not be adjusted by unblinded investigators after the point of randomisation.

In line with current guidelines, every effort will be made to address all relevant cardiac and non-cardiac comorbidities. Given the diverse nature of comorbidity and randomised design of REPRIEVED, specific guidelines will not be provided for the treatment of these comorbidities. Data on the prescription of relevant cardiovascular medications will be collected via the electronic case report form (eCRF).

As detailed above, no medications are currently licensed specifically for the management of ischaemia or ischaemic symptoms in patients with HFpEF. There are also concerns that many anti-ischaemic therapies may worsen symptoms or outcomes in HFpEF. The use of beta blockers has been associated with an increase in heart failure hospitalisation in observational studies. Long-acting oral nitrates

reduced patient activity and did not improve quality of life in patients with HFpEF in the NEAT-HFpEF trial. International guidelines recommend against the prescription of nondihydropyridine calcium channel blockers due to concerns about worsening heart failure outcomes. Consequently, it is not recommended that patients in REPRIEVED are prescribed these agents for their anti-ischaemic effects. Where patients have already been initiated on these medications, their use will be recorded but not adjusted by the trial team.

## 6.8 Blinding

Effective blinding is necessary to ensure that any observed difference between groups in quality of life is not related to placebo effect.

